A Food Additive Removal Diet for Pediatric Eosinophilic Esophagitis (FREE)

Principal Investigator: [name]

Funded by: Anonymous Donor to the Nemours Foundation

Version Number: v.13

22JUL2020

Summary of Changes from Previous Version:

Affected Section(s)	Summary of Revisions Made	Rationale
1-9	
v.2
 Eliminated SST group. Eliminated previously required 8- week PPI trial. Added 4 week PPI washout period. Added 12 week swallowed steroid washout period. Extended duration of treatment to 12 weeks	ESPGHAN guidelines on EoE have recently changed. The diagnosis of PPIREE has been retracted as it is histologically indistinguishable from EoE. Therefore, PPIs are considered a treatment option, not a diagnostic prerequisite. Comparison of two diets and randomization to both groups ensures a comparison of the effects of eliminating additives vs traditional elimination diets, ensures equal allocation to groups, and reduces selection bias. A PPI and steroid washout period is recommended to determine the true severity of the esophagitis.
1,2,8	
v.3
 Removed the additional biopsy	Investigators at our satellite sites expressed slight concern regarding the need to take an additional biopsy. The biopsy was dropped from the protocol as it was intended for future research and was not critical to this study.
5.1	
v.4
 Limited time since diagnostic biopsy	To minimize changes in the eosinophil count since time of biopsy. Eight weeks was allowed because this is a realistic time frame for the next expected visit after the biopsy is taken.
1-4, 6, 8-9	Changed the nature and names of the diets	The feasibility of the diets was of some concern to the team, particularly difficulty recruiting, high drop-out, and

		
the potential for nutritional deficiencies given that formula would not be allowed. Therefore, the study will compare a dairy free diet to dairy free plus additive free diet given that dairy accounts for the majority of allergic reactions. This will make the diets much more acceptable/feasible to the patients/parents and will still answer the question of whether food additives play a role in EoE.


5.3, 8.0
	
v.5
 
Added language to clarify the role of the local vs the central pathologist
	
Local pathologists will identify patients with >15 eos/hpf. There will only be one central pathologist (review by two pathologists was previously planned but determined impractical). Samples from standard of care biopsies will be batch shipped to the central pathologist and shipped back to originating sites after analysis.

5.1
	
Changed the window since the diagnostic biopsy to 12 weeks
	
An 8 week window for the diagnostic biopsy was considered too restrictive by some team members due to practical issues with scheduling follow up visits.

10.1.4.3
	
Removed language regarding storage of samples
	
Samples will not be stored for future research use

1.1, 5.2
	
v. 6
 
Removed exclusion criteria for anaphylactic food allergies
	
This criteria was too restrictive as the majority of EoE patients have one or more food allergies

1.1, 5.2	v.7	Allowed inhaled steroids. Specified washout period for prednisone, fluticasone and budesonide
1.1, 5.2	v.8 Expanded the age range	Allows the inclusion of patients over age 17
1.1, 5.1, 5.2	v. 9 Expanded the age range removed the PPI washout period requirement removed the exclusion regarding food impaction	Allows the inclusion of patients 3 to 18 Allows the inclusion of patients that have not responded to PPI without the required 4 week washout Allows the inclusion of patients with food impaction
5.2, 8	v. 10 Added dietician follow up calls to description of procedures. Added current PPI use to exclusion criteria (previous protocol identified PPIs as a medication that was not allowed but this was not in the list of exclusion criteria). Added previously failed or currently on dairy elimination therapy to the exclusion criteria.	The protocol now includes previously omitted information
1.1, 10.1	v. 11 Adding the option of consenting over the phone/remote participation	Allows remote recruitment
5.1	v. 12 Changing the age range to ≥ 2 years to 18 years	Allows the inclusion of children age 24 months to 3 years

1.2, 1.3, 8	v. 13 Removed all language pertaining to 24 hour diet recalls (NASR)	The 24 hr diet recalls were discontinued
--------------------	--	--

Table of Contents

1	PROTOCOL SUMMARY.....	1
1.1	Synopsis.....	1
1.2	Schema.....	2
1.3	Schedule of Activities.....	4
2	INTRODUCTION.....	5
2.1	Study Rationale.....	5

1 PROTOCOL SUMMARY

1.1 SYNOPSIS

Title:	Food Additive Removal Diet for Pediatric Eosinophilic Esophagitis (FREE)
Study Description:	Prospective, pragmatic standard of care clinical trial comparing dietary therapies of dairy elimination diet (DED) to dairy + food additive elimination diet (FREE) in children with eosinophilic esophagitis.
Objectives:	
Primary Objective: To compare histologic outcomes (eosinophils per high power field: eos/hpf) of dairy elimination diet (DED) to dairy + food additive elimination diet (FREE) in children with eosinophilic esophagitis.
 
Secondary Objective: To compare endoscopic outcomes (Eosinophilic Esophagitis Endoscopic Reference scores: EREFs) of dairy elimination diet (DED) to dairy + food additive elimination diet (FREE) in children with eosinophilic esophagitis
 
Tertiary Objectives: To compare symptomatic (Pediatric Eosinophilic Esophagitis Symptom Severity Module v2.0: PEES) and quality of life (Peds-QL EoE Module 1) outcomes of dairy elimination diet (DED) to dairy + food additive elimination diet (FREE) in children with eosinophilic esophagitis

Endpoints:	
Primary Endpoint: (1) Histologic change differences of maximum eos/hpf baseline vs 12 week endoscopy
 
Secondary Endpoint: (1) EREFs: Eosinophilic Esophagitis Endoscopic Reference Score baseline vs 12 weeks
 
Tertiary Endpoints: (1) Patient Reported Outcomes (Pediatric Eosinophilic Esophagitis Symptom Severity Module (PEES) baseline vs 12 weeks, (2) quality of life (PedsQL-EoE)¹ baseline vs 12 weeks

Study Population:	We will plan to enroll 72 patients. Based on histologic primary outcome efficacy estimates of DED (50%) compared to FREE (estimated 70%) and a sample size of 36 enrolled patients per group (72 total) with 88% power, we will be able to demonstrate a detectable difference of 30% among two

	
group comparisons. We estimate a 20% drop out rate among the diet elimination groups and analysis based on intention to treat.
 
Patients ≥ 2 - 18 years of age with isolated esophageal eosinophilia (≥ 15 eos/hpf). Patients with peripheral eosinophilia $> 1,500 \mu\text{L}$, concomitant GI inflammatory conditions, history of upper GI tract surgery (e.g. fundoplication), acid reflux by pH probe, severe developmental delay, have other medical conditions likely interfere with the study, has a significant psychiatric condition, has taken swallowed steroids in the last 8 weeks, or are not fluent in spoken and written English will be excluded.

Description of Sites/Facilities Enrolling Participants:
	
Participants will be enrolled nationally.

Description of Study Intervention:
	
Once patients meet eligibility criteria, they will be randomized to DED or FREE study groups. Participants will receive dietary education. Lead dietitians from each site will be identified and the approaches to dietary education will be standardized. Dietary education will be completed at the baseline visit and during follow up phone calls throughout the study.

Study Duration:
	
We anticipate this study will take 30 months to complete.
 
[December 31, 2017-----July 31, 2020]
 
Pre-trial Activities [-----] 7 mos
 
Enrollment/Intervention [-----] 16 mos
 
Data Collection [-----] 19 mos
 
Data Analysis [-----] 4 mos

Participant Duration:
	
Each participant will complete all study visits in 12 weeks +/-14 days.

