9 STATISTICAL CONSIDERATIONS

9.1 STATISTICAL HYPOTHESES

Based on histologic primary outcome efficacy estimates DED without PPI therapy (50%) compared to FREE (estimated 70%) a sample size of 36 enrolled patients per group (72 total) with 88% power, we will be able to demonstrate a detectable difference between the three groups, we assume the standard deviation for both groups to be 30%. We hypothesize that changes in primary and secondary endpoints for FREE participants will be superior to DED.

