9.4 STATISTICAL ANALYSES

Primary analyses will assess effectiveness endpoints, including eos/hpf and EREFs. Efficacy variables will be summarized descriptively and compared between treatment groups.

Secondary analyses include descriptive statistics of the patient population (patient demographics, clinical characteristics, and comorbid conditions), concomitant medications used in this patient population and changes to these treatments.

Categorical variables will be described using frequencies and percentages while continuous variables will be described using means, standard deviations, medians, and inter-quartile ranges.

Independent sample t-tests will be conducted to compare outcomes between groups.

Additional analysis plans may be developed based on clinical considerations.

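### The Synopsis gives 30% as the difference detectable at 88% power, but its own rates differ by 20 points and Section 9.1 uses 30% as the standard deviation; the two sizing statements cannot both be right

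*Combined protocol and SAP*

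**What the plan says.** There are two sizing statements.

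- **Section 1.1, Synopsis (Study Population).** It takes "efficacy estimates of DED (50%) compared to FREE (estimated 70" per cent) with "a sample size of 36 enrolled patients per group (72 total"), and concludes that "with 88% power, we will be able to demonstrate a detectable difference of 30% among two" group comparisons. It gives no SD.
- **Section 9.1, Statistical Hypotheses.** It starts from the same figures: "DED without PPI therapy (50%) compared to FREE (estimated 70%) a sample size of 36 enrolled patients per group (72 total) with 88% power". It mentions a detectable difference but gives no value for it, and refers to three groups in a two-arm trial. It then adds: "we assume the standard deviation for both groups to be 30" per cent.

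Neither place states alpha or sidedness. The hypothesis in Section 9.1 is directional: "changes in primary and secondary endpoints for FREE participants will be superior to DED". Section 9.4 names the test: "Independent sample t-tests will be conducted to compare outcomes between groups". Section 9.2 attributes the sample size to a pragmatic estimate of available patients.

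The outcome scale behind 50% and 70% is not stated. The Synopsis defines the primary endpoint as a change in maximum eos/hpf, which is continuous. Section 3 defines treatment success as fewer than 15 eos/hpf, and Sections 2.2 and 4.2 cite figures of up to 50% for dairy elimination as remission or response rates.

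**The concern.** The same figure, 30%, is a detectable difference in one statement and an SD in the other, while the rates, sample size and power are identical. Within the Synopsis sentence alone, the assumed rates are 20 points apart and the difference said to be detectable is 30.

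The detectable difference is what a reader uses to interpret a null result. Read literally, the Synopsis describes a trial built for an effect 1.5 times the one it expects (30/20). Read with Section 9.1, the trial is built for about 20 points. A reader cannot tell which applies. Because Section 9.2 ties the sample size to patient availability, the sizing sentence is the plan's only statement of what 72 patients can show.

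**Working it through.** **Inputs.** Rates 50% and 70%, 36 per group, power 88% (Synopsis and Section 9.1); SD 30 (Section 9.1); two-sample t-test (Section 9.4). Assumed: alpha 5%, tried one-sided and two-sided, and all 36 per group analysed.

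**1. Reproduce the printed 88%.** Standard error of the difference = SD × √(2/n) = 30 × √(2/36) = 7.07. For 20 points, 20/7.07 = 2.83.

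- One-sided 5%, normal approximation: Φ(2.83 − 1.645) = 88.2%; exact t-test 87.6%.
- Two-sided 5%: Φ(2.83 − 1.960) = 80.7%; exact t-test 79.7%.

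So 88% follows from 20 points, SD 30 and a one-sided 5% test. By the normal approximation that combination needs exactly 36 per group.

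**2. Treat 30 as the difference, keeping SD 30.** 30/7.07 = 4.24. The t-test gives 99.5% (one-sided) or 98.7% (two-sided). By the normal approximation, 88% power would need only 16 or 20 per group.

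**3. Solve for the difference detectable at 88%.** Normal approximation: (z for alpha + 1.175) × 7.07, which gives (1.645 + 1.175) × 7.07 = 19.9 points one-sided and (1.960 + 1.175) × 7.07 = 22.2 two-sided. The exact t-test gives 20.1 and 22.5. Neither is near 30.

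**4. Ask what SD would make 30 points right.** For the t-test, 30 points at 88% with 36 per group needs an SD of 44.7 (one-sided) or 40.0 (two-sided), against the 30 in Section 9.1. Power for the 20 points would then be 59.3% or 55.2%.

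**5. Treat the percentages as response rates.** With 36 per group (range = pooled to unpooled normal approximation):

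| Comparison | One-sided 5% | Two-sided 5% |
|---|---|---|
| 50% vs 70% (20 points) | 54–55% | 41–42% |
| 50% vs 80% (30 points) | 86–88% | 77–80% |

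An unpooled one-sided calculation for 50% versus 80% gives 87.8%, which also rounds to 88%. On this scale an SD of 30 does not apply: the SDs are √(0.5 × 0.5) = 50 points and √(0.7 × 0.3) = 46 points.

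**The case against.** A detectable difference need not equal the hypothesised one, so a 30 beside a 20-point expectation is not by itself an error. There is also a calculation that yields it: 50% versus 80%, unpooled and one-sided, gives 87.8%. That route and the route through 20 points with SD 30 both need the same unstated one-sided 5% alpha, so the arithmetic does not decisively separate them. This stands, and the origin of the 30% is not proven. It does not rescue the text, because an 80% rate for FREE appears nowhere, contradicts the 70% in the same sentence, and leaves the SD in Section 9.1 without a role.

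A second objection is that replacing 30 by 20 could make matters worse. If 50% and 70% are response rates, a gap near 30 points is close to what 36 per group can detect, and 88% beside a 20-point difference would overstate power considerably. This also stands, and it is why the whole sentence has to be restated.

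A third is that the impact is limited: Section 9.2 bases the sample size on availability, and no decision rule in Section 9 uses the detectable difference. That is true. It limits the matter to how results are read, and does not make the two statements consistent.

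**Conclusion.** The point holds. Under the plan's own SD and t-test, 30% cannot be the difference detectable at 88% power with 36 per group: that difference is 20.1 points (one-sided 5%) or 22.5 points (two-sided 5%), and 30 points has about 99% power. The likeliest explanation is that the SD was mislabelled as the difference; a separate 50% versus 80% responder calculation remains possible.

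A reader might infer three stronger things that the documents do not support:

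- **That the slip is certainly a misplaced SD.** The alternative route to 88% prevents that conclusion.
- **That the 88% is wrong.** It reproduces for 20 points with SD 30 if the test is one-sided at 5%. It is unsupported without that statement, and falls to about 80% if the test is two-sided.
- **That the trial is underpowered for its own hypothesis.** That follows if the rates are response rates (41–55% power for 20 points) or if 30 points really is the detectable difference (55–59%). The documents do not settle either.

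The figures rest on an assumed 5% alpha and on all 36 per group being analysed. The 20% dropout stated in the Synopsis is a separate matter.

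**What to change.** Decide which calculation was run, then print one sizing sentence, identical in the Synopsis and Section 9.1. It should name the outcome scale, difference, SD where one applies, alpha and sidedness, and give the power that follows at 36 per group.

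- **If the outcome is continuous on a percentage scale with SD 30:** remove the 30% detectable difference and give the difference as 20 points with SD 30. Print 88% only with a one-sided 5% test, or about 80% with a two-sided 5% test.
- **If 50% and 70% are response rates:** drop the SD of 30%. For 20 points print about 41–42% (two-sided 5%) or 54–55% (one-sided 5%). A 30-point gap (50% versus 80%) may be quoted beside it at 77–80% or 86–88%. Name the test for proportions as well, since Section 9.4 names only the t-test.

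In either case, change three groups to two groups in Section 9.1.

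The cost is one sentence in each of two sections, plus naming a test in Section 9.4 if the response-rate version applies. Enrolment and study procedures are unchanged.

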1.2 SCHEMA

1.3 SCHEDULE OF ACTIVITIES

Procedures	Screening Day -7 to 1	Enrollment/Baseline Visit 1, Day 1	Study Visit 2 (FUP Call) Day 7 (week 1) +/-2 days	Study Visit 3 (FUP Call) Day 14 (week 2) +/- 2 days	Study Visit 4 (FUP Call) Day 21 (week 3) +/-2 days	Study Visit 5 (FUP Call) Day 28(week 4) +/-2 days	Study Visit 6(FUP Call) Day 35 (week 5) +/-2 days	Study Visit 7 (FUP Call) Day 42 (week 6) +/-2 days	Study Visit 8 (FUP Call) Day 49 (week 7) +/-2 days	Study Visit 9 Day 56 (week 8) +/-14 days	Study Visit 10 Day 63 (week 9) +/-14	Study Visit 11 Day 70 (week 10) +/-14	Study Visit 12 Day 77 (week 11) +/-14	Study Visit 13 Day 84 (week 12) +/-14
Informed consent	X													
Review Inclusion/Exclusion Criteria	X													
Medical History	X													
Demographics		X												
Pathologist Questionnaire / Peak Eosinophils per high power field (Eos/hpf)	X													X
Randomization		X												
Personal Information		X												
Height and Weight		X												X
Eosinophilic Esophagitis Endoscopic Reference Score (EREF)		X												X
Diet Education		X												
Dietician Follow Up Calls			X			X			X				X	
Three-day Diet Diary		X												X
Quality of Life (PedsQL EoE)(Parent & Child)		X				X*				X*				X*
Pediatric Eosinophilic Esophagitis Symptom Severity Module (PEESS)(Parent & Child)		X				X*				X*				X*
Adverse Event Reporting (Safety Q)		X				X*				X*				X*

Procedures	Screening Day -7 to 1	Enrollment/Baseline Visit 1, Day 1	Study Visit 2 (FUP Call) Day 7 (week 1) +/-2 days	Study Visit 3 (FUP Call) Day 14 (week 2) +/- 2 days	Study Visit 4 (FUP Call) Day 21 (week 3) +/-2 days	Study Visit 5 (FUP Call) Day 28(week 4) +/-2 days	Study Visit 6(FUP Call) Day 35 (week 5) +/-2 days	Study Visit 7 (FUP Call) Day 42 (week 6) +/-2 days	Study Visit 8 (FUP Call) Day 49 (week 7) +/-2 days	Study Visit 9 Day 56 (week 8) +/-14 days	Study Visit 10 Day 63 (week 9) +/-14	Study Visit 11 Day 70 (week 10) +/-14	Study Visit 12 Day 77 (week 11) +/-14	Study Visit 13 Day 84 (week 12) +/-14
Concomitant medication review	X	X		X	X		X	X		X			X	X
Coordinator Call				X	X		X	X		X	X		X	
Payment to Part. for Completed Visit		X				X				X				X

* REDCap survey – completed by participant/parent

2 INTRODUCTION

2.1 STUDY RATIONALE

Eosinophilic Esophagitis (EoE) is a food antigen driven inflammatory condition that continues to increase in prevalence. Commonly used food additives have been shown to promote intestinal inflammation in animal models², yet research is needed to further assess the impact of food additives on inflammatory conditions in humans. We hypothesize that dairy + food additive elimination (FREE) will show improved efficacy when compared dairy elimination alone (DED).

2.2 BACKGROUND

Eosinophilic esophagitis (EoE) is a chronic allergen driven inflammatory disorder histologically characterized by the abnormal infiltration of eosinophils in the esophagus (maximum eosinophil count ≥ 15). Primary symptoms manifest while eating and include dysphagia, chest pain, and food impaction. EoE was first described in the 1990s, but is increasingly recognized worldwide. It affects both adults and children with an estimated prevalence of 56.7/100,000.³

The treatment of EoE aims to reduce inflammation, thereby reducing symptoms. The recommended clinical pathway for the initial treatment of EoE includes high-dose proton pump inhibitor (PPI) therapy followed by either topical steroids or elimination diet in patients unresponsive to PPIs.⁴

PPIs: The relationship between acid suppression and EoE is unclear. Nevertheless, a subset of EoE patients are responsive to acid suppression medications such as PPIs (a condition referred to as Proton Pump Inhibitor Responsive Eosinophilic Esophagitis or PPIREE).^{5,6} PPIs may benefit patients with EoE by

reducing acid or by an unclear anti-inflammatory mechanism. Because some patients are responsive to PPIs, the diagnosis of eosinophilic esophagitis has included the demonstration of persistent esophageal eosinophilia after a two-month course of high dose PPI therapy.⁴ However, ESPGHAN guidelines have recently changed and the diagnosis of PPIREE has been retracted as it is histologically indistinguishable from EoE. Therefore, PPIs are considered a treatment option, not a diagnostic prerequisite.

Steroids: Oral steroids, such as budesonide, are a preferable alternative to systemic steroids that have numerous and well documented adverse effects. Oral topical steroids have anti-inflammatory effects (i.e., fluticasone or budesonide, swallowed rather than inhaled, for an initial duration of 8 weeks) and are, therefore, another first-line pharmacologic therapy for the treatment of EoE.⁷

With the use of budesonide, studies show significant histological and symptomatic remission in 80-90% of patients.⁸⁻¹¹ Unfortunately, symptoms recur when steroids are discontinued. Although the majority of evidence suggests that adverse effects of short-term budesonide use are not common¹², several studies concluded that children treated with oral budesonide for one to six months experienced adrenal suppression.¹³⁻¹⁵

Dietary Treatments: Given that EoE is thought to be an antigen/immune-mediated disease, elimination diets are considered logical and safe first-line treatment options. Elimination diets focus on the removal of the allergens most likely to evoke the inflammatory response. Recent studies have demonstrated a response to elimination diets in 30-60% of EoE patients.^{16,17} The diets, however, vary regarding the number and types of foods eliminated. Three main strategies evolved in the last decade: (1) the elemental diet, which uses exclusively amino acid enteral formula, (2) the skin prick testing directed diet, which eliminates foods with positive allergy testing, and (3) empiric elimination in which the most common allergenic foods are avoided.²⁰ The elemental diet, although highly effective in inducing remission, is impractical for long term use given its high cost. In addition, refraining from eating any solid foods for an extended period of time is extremely difficult. Results regarding allergen directed diets have been mixed¹⁷ presumably because of the lack of reliability and specificity of allergy tests. Therefore, empirical elimination diets might be the easiest treatment option to implement and to maintain.

Elimination Diets and EoE: Studies have shown that a six-food elimination diet (6FED)(cow's milk, wheat, peanuts and tree nuts, soy, and fish/shellfish) induces remission in most children and adults with EoE¹⁷ but that only one in four patients sustain remission at nine months. Patients tend to relapse because the diet is difficult to follow and very restrictive. In addition, the 6FED includes a complex plan for the reintroduction of foods over specified time frames. A four-food elimination diet (4FED)(cow's milk, wheat, egg, and soy) is far less restrictive and more likely to encourage adherence. In addition, these four food groups appear to be the most commonly associated with the inflammatory response in EoE patients.¹⁹⁻²⁰ Preliminary studies report a 54% histological remission rate with 4FED.²⁰⁻²² However, studies also show a 30-50% remission rate when eliminating dairy alone. More research is needed before concluding which diet is reliably effective in the majority of EoE patients.

The widespread use of food additives in modern-day diets might contribute to the increased incidence of inflammatory diseases such as EoE. Food additives are substances added during

production, processing, packaging, or storage of food products. They are intended to enhance or preserve flavor, appearance, and durability. Some food additives are natural (e.g. vinegar for pickling, salted ham), but the additives of concern here are the artificial ones more recently introduced into the food supply.

Commonly used artificial food additives have been shown to promote intestinal inflammation in animal models². In addition, food additives are excluded from some diets that induce remission in Crohn's disease. In fact, the lack of food additives is likely one of the reasons enteral nutrition is so effective. As inflammatory bowel disease and eosinophilic esophagitis share GI tract mucosal immune dysregulation, dietary intervention with anti-inflammatory properties may be of benefit for patients with EoE.

There is a need to establish optimal treatment pathway(s) not only for the initial remission of EoE, but also for the long-term maintenance of remission. The adverse effects of long-term PPI and SST therapy are unknown. In addition, adherence rates to medications and to highly restrictive diets are poor. Elimination diets such as 4FED and FREE are less restrictive than other diets, which might improve outcomes. A preservative-free diet for EoE has not been evaluated. Finally, the current literature does not address patient reported outcomes or patient reported quality of life, which might be associated not only with efficacy, but also with rates of adherence, thereby impacting the sustainability of treatment.

